4.2.1.1 Definition of the MTCA

Several radioactivity amounts of ¹⁷⁷Lu-3BP-227 are planned to be tested according to an adaptive radioactivity escalation plan. Each subject will only participate in one part of the protocol. The purpose of the radioactivity escalation part is to determine the MTCA. If not feasible, the maximum tolerated single activity (MTSA) or the maximum administered cumulative activity (MACA) will be determined according to the situation below:

- The MTCA is defined as the maximum tolerated cumulative activity that may be administered following fractionated i.v. administrations of at least 4 weeks apart, so that:
 - No more than 33% of the subjects experience a DLT during Cycles 1 and/or 2 (see DLT definition in Section 4.7.1.1), and
 - The cumulative radiation in each target organ does not exceed the acceptability limits (see Section 4.7.1).
- The MTSA is defined as the highest single radioactivity that can be given so that no more than 33% of the subjects experience a DLT during Cycle 1. The MTSA will be determined in case of unacceptable toxicity seen after Cycle 1.
- The MACA will be determined if the MTCA is not reached during the dose escalation part.

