19.5.1 Statistical Model

After study screening procedures, eligible subjects will receive up to 2 i.v. administrations of 177 Lu-3BP-227 in two consecutive treatment cycles 4 weeks apart. A range of doses will be tested, including possibly 2.5, 3, 3.5, 4, 4.5, 5, 5.5, 6, 6.5, 7 and 7.5 GBq per cycle. Additional or alternative dose levels may be chosen. These possible dose levels are labelled as d=1, ..., N, where N is the maximum number of dose levels for the study.

The analysis is based on a method reported by Guede et al.[9] and Tibaldi et al. [37].

If, during Cycle 1, a subject receives dose d_1 and in Cycle 2 dose d_2 , the probability, p, of observing a subject with DLTs up to 4 weeks after the two cycles of dosing is modelled as a function of dose as:

logit
$$(p) = \text{logit } (p_0) + \frac{\text{logit } (33\%) - \text{logit } (p_0)}{MTSA} d_1 + \beta * d_2$$

where p_0 , MTSA and β are the model parameters having the following interpretation:

- p_0 is the probability of observing DLTs under placebo ($d_1=d_2=0$),
- MTSA is the maximum tolerated single activity, being defined as the dose d₁ at which the predicted probability of DLTs is 33% for dosing Cycle 1 (single dose), and
- β is a slope coefficient indicating the impact of a second dose d_2 on DLT probability.

The prior distribution on p_0 , MTSA and β determine the prior distribution on the probability of DLT as a function of up to two doses. For cycle 1 data analysis, the dose d_2 is set to zero. So, only parameters p_0 and MTSA are involved. β is involved when subjects undergo their second cycle. A positive β indicates an increase in DLT probability with second dose.

The MTCA is defined as the maximum tolerated cumulative activity $(d=d_1+d_2)$, where $d_1=d_2$) that may be administered following fractionated i.v. administrations of the same dose d_1 at least 4 weeks apart so that no more than 33% of the subjects experience a DLT during Cycles 1 and/or 2.

The MTCA can be presented as a derived parameter from the logistic regression model. It is expressed as:

$$MTCA = 2* MTSA * \frac{\text{logit } 33\% - logit }{\text{logit } 33\% - \text{logit } p_0 + \beta * MTSA}.$$

The MTCA will be equal to twice the MTSA when β equals 0 (i.e. the DLT probability is not changed after a second dose). When the DLT probability is increased (β >0), the MTCA will be decreased (and vice versa).

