During the study, the target organ exposure will be monitored after each dose and doses may be adapted if the exposure exceeds organ-specific maximum acceptability limits. As such, if the predicted MTCA exceeds the maximum acceptability limits for target organ exposure, the maximum radioactivity dose will be used instead. This feature was not considered in the simulation study, where it was assumed that a cumulative dose up to 15 GBq would induce an acceptable organ exposure.

Prior distributions were elicited based on historical knowledge about the placebo DLT rate and the MTSA target. The following prior distributions are used in the trial:

$$p_0 \sim beta(a=1,b=9)$$
,
MTSA $\sim gamma$ (shape = 4, rate = 0.5),
and

 $\beta \sim normal \ (\mu = 0, sd = 0.25).$

Based on these distributions, 20 dose-DLT curves from the prior distribution were simulated after Dose 1 (black) and after Dose 1 and 2 (red) (see Figure 3). The prior probability distributions for the MTSA is summarised in Table 10. The prior probability distributions for the MTCA is summarised in Table 11

[figure not shown]

Figure 3 40 Random Observations (Curves) from the Prior Distribution

Table 10 Prior Probability Distribution of MTSA

Dose range for Cycle 1	Prior MTSA probability
2.5 GBq	5.2%
2.5 to 5 GBq	20.6%
5 to 7.5 GBq	28.6%
>7.5 GBq	45.6%

MTSA=Maximum tolerated single activity.

Table 11 Prior Probability Distribution of MTCA

Dose range (cumulative)	Prior MTCA probability
≤5 GBq	32.5%
5 to 10 GBq	24.6%
10 to 15 GBq	15.7%
>15 GBq	27.2%

MTCA= Maximum tolerated cumulative activity.

Given any set of data, the prior distribution can be updated, yielding a posterior distribution of the parameters. From this posterior distribution many different quantities of relevance can be calculated:

- $E(p|d_1, d_2)$ =Posterior mean probability of DLT for Cycle 1 dose d_1 and Cycle 2 dose d_2 .
- TS_d=(tolerable) Probability that the DLT rate is below 0.33, $Pr(p \le 0.33 | d,0)$, for a Cycle 1 dose d (d₂=0).
- QS_d=Probability of Cycle 1 dose d being the maximum dose where $E(p|d,0) \le 0.33$.
- TC_d=(tolerable) Probability that the DLT rate is below 0.33, $Pr(p \le 0.33 | d/2,d/2)$, for a cumulative dose d (d₁=d₂=d/2).
- QC_d=Probability of cumulative dose d being the maximum dose where E(p|d/2,d/2) <0.33.

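### The Attachment 5 prior puts half its mass on a negative second-dose slope, which the model's own definition rules out; this understates two-cycle DLT risk and makes the derived MTCA incoherent

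*Protocol*

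**What the plan says.** Protocol section 19.5.1 models p, the probability "of observing a subject with DLTs up to 4 weeks after the two cycles of dosing", on the logit scale with a term in the Cycle 1 activity d1 and a term β·d2 for the second. The same equation gives the Cycle 1 risk: "For cycle 1 data analysis, the dose d_2 is set to zero". The MTCA is the equal-fraction cumulative activity at which "no more than 33% of the subjects experience a DLT during Cycles 1 and/or 2", in line with section 4.2.1.1. On the slope, the text says "A positive β indicates an increase in DLT probability with second dose". It adds that β = 0 makes the MTCA twice the MTSA, and then: "When the DLT probability is increased (β >0), the MTCA will be decreased (and vice versa".

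The prior on β is normal with mean 0 and SD 0.25, with no sign constraint. Section 19.5.1 refers to historical knowledge for the placebo DLT rate and the MTSA, and offers no such basis for β. No likelihood is written out. Section 12.2.4 carries the same priors into the final analysis, with noninformative priors as a sensitivity check.

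**The concern.** By these definitions p(d1, 0) is the risk of a DLT in Cycle 1, and p(d1, d2) is the risk of a DLT in Cycle 1 or Cycle 2 at the same d1. The second event contains the first, so p(d1, d2) ≥ p(d1, 0), which requires β ≥ 0. Half the prior breaks this ordering, and no reason is given for allowing it.

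The data can push the same way. Subjects with a Cycle 1 DLT are discontinued before Cycle 2 (section 19.5.2), so Cycle 2 outcomes come only from subjects who tolerated Cycle 1. The model can read an uneventful second cycle as protection.

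At stake are the MTCA, which is the phase I primary endpoint (section 4.4.1.1) and the ceiling on phase II activity (section 4.3), and the section 19.5.2 rule that uses the MTCA to decide whether the Cycle 2 fraction is repeated or reduced.

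**Working it through.** **Inputs (section 19.5.1).** p0 ~ Beta(1, 9); MTSA ~ gamma with "shape = 4, rate = 0.5"; β ~ normal, mean 0, SD 0.25. Write L = logit(0.33) − logit(p0). Then

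- logit p(d1, d2) = logit(p0) + (L/MTSA)·d1 + β·d2
- MTCA = 2·MTSA·L / (L + β·MTSA)

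**1. Reproducing Table 11.** Four million prior draws through the printed ratio give:

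| MTCA (GBq) | Table 11 | Printed ratio, negatives counted as ≤5 | Negative-denominator draws counted as >15 |
|---|---|---|---|
| ≤5 | 32.5% | 31.6% | 14.9% |
| 5-10 | 24.6% | 25.7% | 25.5% |
| 10-15 | 15.7% | 15.7% | 15.6% |
| >15 | 27.2% | 27.0% | 44.0% |

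The first calculation matches to within 1.1 points; the second (which also sets draws with p0 above 33% to 0) does not. Genuinely positive values up to 5 GBq make up only 13.3% of draws. Negative values make up 18.3%, and 13.3% + 18.3% = 31.6%. Of the negative draws, 17.1 points have L > 0 with β so negative that L + β·MTSA < 0. The remaining 18.3 − 17.1 = 1.2 points are draws with p0 above 33%, where the numerator is negative.

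**2. Prior mass on the impossible region.** P(β < 0) = Φ(0) = 50%.

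**3. One set of values by hand.** Take p0 = 0.10 and MTSA = 8. Then L = −0.708 + 2.197 = 1.489, and logit p(7.5, 0) = −2.197 + (1.489/8)×7.5 = −0.801, so Cycle 1 risk is 31.0%.

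- β = −0.1: logit p(7.5, 7.5) = −0.801 − 0.75 = −1.551, so two-cycle risk is 17.5%. MTCA = 16×1.489/(1.489 − 0.8) = 34.6 GBq, against 16 at β = 0.
- β = −0.2: the denominator is 1.489 − 1.6 = −0.111, and the MTCA is about −215 GBq.

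**4. Prior averages.** Given β < 0, two-cycle risk lies below Cycle 1 risk by 4.9 points on average at 2.5 GBq per cycle and by 18.8 points at 7.5. The prior probability that two-cycle risk is at most 33% at 2×7.5 GBq is 45% as written and 11% if β is half-normal at the same SD.

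**5. Direction for the MTCA.** The printed ratio exceeds 2×MTSA in 31.7% of draws. Given β < 0, 38% of draws fall in the ≤5 row and 43% in the >15 row; given β ≥ 0 the figures are 25% and 11%. Negative slopes inflate both tails.

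**6. With data.** Two likelihood readings were used because the protocol gives none: one record per subject, and separate Cycle 1 and Cycle 2 records.

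- Example: 0/3 with a DLT at each of the three lower levels, one Cycle 1 DLT in 4 at each of 6.5 and 7.5 GBq, and no Cycle 2 DLT. The model gives a Cycle 1 risk at 7.5 GBq of 22-44% and a two-cycle risk of 6-8%.
- Simulated data: 3 subjects at each of the five planned levels, Table 12 risks taken as cumulative, no adaptation. Mean posterior two-cycle risk at 15 GBq, range over the two readings:

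| Scenario | True risk | As written | β half-normal, SD 0.25 |
|---|---|---|---|
| A | 14% | 7-9% | 22-31% |
| B | 35% | 21-26% | 33-42% |
| C | 64% | 36-45% | 50-59% |

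**7. The plan's own simulations.** Table 13 median MTCA against the truth stated in section 19.5.3: A 17.4 vs 30 (−42%), B 14.7 vs 14 (+5%), C 9.5 vs 9 (+6%), D 4.2 vs 2 (+110%), E 6.2 vs 5 (+24%). D cannot be attributed to β: Table 12 gives it 46% after one 2.5 GBq dose and 46% after two, which implies MTCA = 2×MTSA = 4, not the stated 2.

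**The case against.** A reader might infer that the prior biases the MTCA upward in general. The documents do not support that. Strongly negative slopes send the printed ratio below zero, Table 11 appears to place those draws in its lowest row, and Table 13 has the median MTCA far below truth in A and only 5-6% above it in B and C.

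A reader might also infer that cohort-to-cohort escalation is driven by the faulty slope. Section 19.5.2 selects the next activity by QS_d, which sets d2 to zero. For Cycle 2, a high MTCA can only leave the fraction unchanged; the rule never raises it. Limits on DLT counts that do not depend on the model apply as well, organ-dose limits apply separately (section 4.7.1), and the SRC makes the final decision (section 12.2.8). The final model is fitted only where possible. All of this stands and limits the reach.

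The cost of a constraint is real too. In Scenarios A and D, Table 12 risks are the same after one and two doses, so the true β is 0 and a half-normal prior must overstate risk. In A, 7-9% as written is nearer the true 14% than 22-31%. The scale therefore has to be tuned.

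Finally, β might have been meant for Cycle 2 risk among subjects free of a DLT after Cycle 1, where a fall is possible. That is not how p or the MTCA is defined. The noninformative priors in section 12.2.4 are not said to constrain the sign of β, so they do not answer the point.

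**Conclusion.** The concern holds as a coherence defect that should be fixed. Under the protocol's definitions β < 0 is impossible, and half the prior lies there. Two-cycle risk was understated in Scenarios A, B and C under both likelihood readings, and prior tolerance at 2×7.5 GBq is 45% rather than 11%. The derived MTCA is incoherent in both directions, with about 17-18% of prior draws negative.

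The 50% and the ordering argument follow from the text alone. The 11% assumes a half-normal prior at the printed SD. The posterior figures assume three subjects per level, no adaptation and one of two unstated likelihoods, so they illustrate direction and rough size and are not operating characteristics of the trial. That Table 11 counts negative values as ≤5 GBq is inferred from the close match, not stated. The consequence is confined to the reported MTCA and the Cycle 2 repeat-or-reduce rule.

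**What to change.** These are changes to the statistical model only:

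- Restrict β to non-negative values (for example half-normal or log-normal), with the scale tuned by simulation so that Scenario A is not badly overstated. Alternatively, model Cycle 2 risk conditional on no Cycle 1 DLT and derive the cumulative risk from it.
- State the likelihood. One coherent form gives p(d1, 0) for a Cycle 1 DLT, p(d1, d2) − p(d1, 0) for a first DLT in Cycle 2, and 1 − p(d1, d2) for none.
- Define the MTCA when L or L + β·MTSA is not positive, and say how such draws are tabulated.
- Rerun Tables 11 and 13, and use the same prior in the section 12.2.4 analysis.

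The cost is a change in model code and a rerun of the simulations, with no additional subjects. The price is more conservative estimates where the second dose truly adds nothing, which is why the scale needs tuning.

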19.5.2 Trial Simulation Details

This section present results of trial simulation study that was performed to determine the operational characteristics of the adaptive dose escalation procedure. The design of that simulation study is very similar to the actual study design, with some changes necessary to enable the automation of trial simulations. The impact of any discrepancy should be negligible.

The trial design involves two sets of rules, namely:

- (1) dose-escalation rules for the next cohort when the current cohort completes Cycle 2, and
- (2) rules for Cycle 2 dosing after completion of Cycle 1.

A cohort will be considered as ended once three subjects of the cohort complete Cycle 2 or early discontinue during Cycle 2. Subjects with DLTs in Cycle 1 will be discontinued prior to Cycle 2.

Once five subjects are enrolled in a cohort, the cohort will be considered as ended, after all five subjects complete Cycle 2 or discontinue early during Cycle 1 or 2.

For the purpose of simulations, the dose decisions will be made at the following milestones:

- Cycle 2 dosing will be determined only once the full cohort, including any replacement subjects, completes Cycle 1 (as opposed to on an individual basis in the study).
- The dose for the next cohort will be decided once the current cohort has ended.

The timing of these decisions will slightly vary during the study, as it is currently planned to decide the Cycle 2 dose on an individual subject basis and to decide for the next cohort once up to three subjects in the current cohort are 3 weeks into Cycle 2. The impact of these changes should be minimal.

The inter cohort dose escalation will be performed as follows:

- (1) The starting dose will be d=5 GBq fractionated into two administrations of $d_1=d_2=2.5$ GBq per cycle and the first cohort will include three subjects.
- (2) If there is no DLT during Cycle 1, the radioactivity for the next cohort will be increased by 3 GBq (1.5 GBq/cycle) up to 11 GBq (5.5 GBq/cycle) and then by 2 GBq (1 GBq/cycle) up to the last planned cohort of 15 GBq (7.5 GBq/cycle). Cohort size will be three subjects.
- (3) If at least one subject in a cohort reports any DLT, wait for the corresponding cohort (including any replacement) to end the study, then fit the Bayesian model to all available Cycle 1 and Cycle 2 data, and select next dose as the dose d at which QS_d is maximum, or the maximum allowed dose if any of the following constraints are met:
 - (a) if there are two DLTs out of three, three DLTs out of five, or three DTLs out of six subjects receiving a single or cumulative dose, d must be lower than or equal to that dose;
 - (b) if there are three DLTs out of three, or at least three DLTs out of four, or at least four DLTs out of five, or at least four DLTs out of six subjects receiving a single or cumulative dose, d must be lower than that dose;
 - (c) dose d must be at most 1 GBq larger than the maximum Cycle 1 dose tested previously.

Repeat steps 2 and 3 again, assigning the subjects/cohort to this dose. Terminate study enrolment when any of the following stopping rules happen:

- A the MTSA is precisely estimated: CV (MTSA) calculated as the inter-quartile range over the median is lower than 30%;
- B maximum possible dose (7.5 GBq) is safe: TS_{7.5}>80% and d₁=7.5 GBq administered;
- C minimum dose tested (2.5 GBq) is toxic: TS_{2.5} <20%;
- D total sample size for next dose is already ≥ 6 .

The MTSA will be declared to be found when study stops for criteria A or D.

Individual dosing decision for the second treatment cycle will be done as follows:

- Subject will be eligible for Cycle 2 only if subject had no DLT during Cycle 1. Subjects with DLTs in Cycle 1 will be discontinued and replaced with a maximum of two replacements.
- The same fractional dose as in Cycle 1 will be repeated during Cycle 2 ($d_2=d_1$), if the dose having the largest probability to be the MTCA is larger than 2 x d_1 .
- The fractional dose for Cycle 2 will be decreased to d₂=MTCA-d₁ dose, if the predicted cumulative exposure after Cycle 2 is above the MTCA target. In this situation, the cumulative exposure after two cycles should not exceed the MTCA.

The study will be terminated when all cohorts have ended the study, as defined above.

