4.2.1.3 Dose Escalation Mode

Dose escalation is planned to proceed in two steps, with two different increments for the radioactivity escalation. In the first step, in order to minimise the number of subjects receiving subtherapeutic activity, the inter-cohort radioactivity escalation will be performed by increment of 3 GBq (1.5 GBq per administration), up to the first study drug related treatment-emergent AE (TEAE) (Grade 2 or higher, except hair loss) or until a DLT occurs. Afterwards, the maximum increment will be reduced to 2 GBq (1 GBq per cycle) for all subsequent cohorts if dose escalation is allowed. However, even if no Grade 2 or higher AE are observed up to a cumulative activity of 11 GBq, radioactivity will be increased by 2 GBq (1 GBq per cycle).

Table 5 illustrates the escalation plan based on the escalation scheme defined above. However, if DLTs are reported, a statistical Bayesian modelling approach will be implemented to produce a more precise dose-DLT curve to guide the dose selection (see details in Attachment 5, Section 19.5) and predict an activity not exceeding the MTCA/MTSA that could be tested in the next cohort.

Planned radioactivity Cohort 1 Cohort 2 Cohort 3 Cohort 4 Cohort 5 escalation Cumulative 5 GBq 8 GBq 11 GBq 13 GBq 15 GBq 2.5 GBq/C 4 GBq/C 5.5 GBq/C 6.5 GBq/C 7.5 GBq/C Per cycle

Table 5 Cohorts and Radioactivity Escalation Plan

C=cycle; GBq=gigabecquerel.

Once the dose escalation has been completed, the MTCA level may be repeated in a last cohort (see Section 4.2.1.4 for stopping rules and Section 4.2.1.1 for MTCA definition). If the MTCA is not reached and if limiting organ dose levels are not exceeded at the highest planned activity (2×7.5 GBq) and if no individual withdrawal criteria are met, an additional cohort (Cohort 6) with three administrations at the highest single administration level may be added (3×7.5 GBq).

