Note that, in this model, the MTSA and MTCA are parameters. They have a probability distribution. A consequence of the Bayesian modelling is the probabilities, QS_d , which is the probability that a dose is the MTSA for Cycle 1 and QC_d , which is the probability that a cumulative fractional dose is the MTCA after Cycle 2. This is a powerful question that cannot be answered from a frequentist perspective.

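### As printed, the model step that picks the next dose after a DLT hardly discriminates: QS_d peaks at 7.5 GBq, and the constraints that then decide the dose omit 2/4 and 2/5 DLTs

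*Protocol*

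**What the plan says.** Protocol 4.2.1.3 states that, once DLTs are reported, a Bayesian model will guide dose selection as detailed in Attachment 5 and will "predict an activity not exceeding the MTCA/MTSA that could be tested in the next cohort".

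Attachment 5 supplies the mechanics. In 19.5.1 the levels are listed: "A range of doses will be tested, including possibly 2.5, 3, 3.5, 4, 4.5, 5, 5.5, 6, 6.5, 7 and 7.5 GBq per cycle". The MTSA is the dose "at which the predicted probability of DLTs is 33% for dosing Cycle 1 (single dose"), with prior Gamma("shape = 4, rate = 0.5"). QS_d is introduced as "Probability of Cycle 1 dose d being the maximum dose where" the posterior mean E(p|d,0) is at most 0.33. A few lines later it is glossed as the quantity "which is the probability that a dose is the MTSA for Cycle 1".

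In 19.5.2, if at least one subject in a cohort has a DLT, step 3 says to "select next dose as the dose d at which QS_d is maximum", unless a constraint binds:
- (a) no escalation "if there are two DLTs out of three, three DLTs out of five, or three DTLs out of six subjects";
- (b) a lower dose after 3/3, at least 3/4, at least 4/5 or at least 4/6;
- (c) at most 1 GBq above the highest Cycle 1 dose already tested.

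The counts 2/4 and 2/5 appear in neither (a) nor (b). Section 19.5.2 also discontinues subjects with a Cycle 1 DLT and replaces them, with at most two replacements. A cohort ends when three subjects complete Cycle 2 or discontinue during it, or when all five enrolled have finished.

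**The concern.** Picking the level with the largest QS_d works only if the levels compete on similar terms. Each level below 7.5 GBq is credited with a 0.5 GBq slice of the MTSA distribution. The top level is credited with everything from 7.5 GBq upward. If the top level wins almost whatever the data, the model contributes little, and the dose after a DLT is set by the hand-written constraints.

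Those constraints then have to be complete, and they are not. At stake is whether the rule behind first-in-human dose recommendations stays within its own 33% limit, and whether the operating characteristics in Table 13 describe the rule as printed.

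**Working it through.** **Inputs (19.5.1).** logit p = logit p0 + [(logit 0.33 − logit p0)/MTSA]·d1 + β·d2, with p0 ~ Beta(1,9), MTSA ~ Gamma(4, rate 0.5), β ~ N(0, sd 0.25), and eleven levels from 2.5 to 7.5 GBq.

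**The plan's own figures.** Exact Gamma probabilities for Table 10 are 3.8 / 20.4 / 27.4 / 48.4%, against the stated 5.2 / 20.6 / 28.6 / 45.6%. The gaps are compatible with a table built from about 1000 draws (chi-square p = 0.07). Table 11 reproduces closely by simulation: 31.6 / 25.7 / 15.7 / 27.0%, against 32.5 / 24.6 / 15.7 / 27.2%. The model is therefore being read as the authors used it.

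**QS_d on the list.** With d2 = 0 and p0 below 0.33, p ≤ 0.33 exactly when d1 ≤ MTSA. (Under Beta(1,9), p0 exceeds 0.33 with probability 0.67^9 = 2.7%.) Hence QS_d = Pr(d ≤ MTSA < d + 0.5) below the top, and QS_7.5 = Pr(MTSA ≥ 7.5).

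**Prior.** Pr(MTSA > x) = exp(−x/2)·Σ(k=0..3) (x/2)^k/k!.
- x = 7.5: exp(−3.75) × (1 + 3.75 + 7.031 + 8.789) = 0.02352 × 20.570 = 0.484.
- Largest lower slice, 5.5 to 6.0: 0.06393 × 10.997 − 0.04979 × 13 = 0.703 − 0.647 = 0.056.

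**Posterior, Cycle 1 data.** Prior draws were weighted by the binomial likelihood, with earlier planned levels at 0/3. Ranges are over current doses of 2.5, 4, 5.5 and 6.5 GBq.

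| DLTs | QS_7.5 | Next largest QS_d |
|---|---|---|
| 1/3 | 0.42–0.72 | 0.06–0.07 |
| 2/4 | 0.33–0.55 | 0.06–0.09 |
| 2/5 | 0.37–0.61 | 0.06–0.09 |
| 3/5 | 0.24–0.40 | 0.07–0.12 |

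The maximum is at 7.5 GBq in every cell. A wider set (eight counts at five doses) gave 7.5 GBq in 40 of 40 cases. Adding five heavier counts gave 56 of 65, and the nine exceptions are all counts that (b) already forces down.

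**A reachable 2/4.** One Cycle 1 DLT, one replacement, then one Cycle 2 DLT among the three who continue: 2/4. Counted instead as 1/4 on the single dose and 1/3 on the cumulative dose, it is still unlisted. Take it at 5.5 GBq after clean cohorts at 2.5 and 4 GBq. QS_d is largest at 7.5 GBq, and (c) cuts that to 6.5 GBq.
- One record per subject (final outcome only): likelihood 1/1 at (5.5, 0) and 1/3 at (5.5, 5.5). QS_7.5 is 0.35, next 0.09. E(p|6.5,0) is about 41%.
- Two records (Cycle 1, then Cycle 2): 1/4 at (5.5, 0) and 1/3 at (5.5, 5.5). QS_7.5 is 0.61, next 0.08. E(p|6.5,0) is about 26%.

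**A reachable 2/5.** Two Cycle 1 DLTs, two replacements, none in Cycle 2, at 5.5 GBq: again 7.5 GBq cut to 6.5 GBq, with mean risk 42% (one record) or 28% (two records).

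**Against the stated purpose.** Section 4.2.1.3 promises an activity not exceeding the MTCA/MTSA, defined by the 33% limit. Under one-record coding the printed rule returns a level whose posterior mean is above it. The text does not say which coding applies.

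**The case against.** Several points on the other side stand.

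- **Pooling is not written out.** Taken literally, the definition uses a posterior mean, so QS_d would not be a probability at all. If the rule is instead read as the highest level with posterior mean at most 33%, the selected level is usually not 7.5 GBq. The gloss as the probability that a dose is the MTSA supports pooling, but does not settle it.
- **Pooling is not the only cause of escalation.** A reader might infer that it alone drives a step up after 2/4 or 2/5. It does not. With Cycle 1 counts, the posterior-mean reading also rises: after 2/4 it gives 4.0 / 4.5 / 6.0 / 7.0 GBq from 2.5 / 4 / 5.5 / 6.5, and after 2/5 it gives the same capped doses as the printed rule. The missing rows contribute independently.
- **Two Cycle 1 DLTs in four is not an end state.** Only two subjects remain, so a fifth enters and the count becomes 2/5 or 3/5. The 2/4 case must run through Cycle 2, where the result depends on coding.
- **Frequency is unknown.** Section 4.7.1.3 describes replacement for reasons other than a DLT, and section 12.1 drops non-DLT dropouts from the evaluation. Four treated with one such dropout and two DLTs is therefore 2/3, which (a) caps.
- **Harm is not shown.** A reader might infer that subjects will be dosed above the target. The text describes a simulation, section 4.2.1.3 uses the model as a guide, steps are capped at 1 GBq, and section 12.2.8 gives the SRC the final decision.
- **Table 13 does not identify the programmed rule.** Re-simulation under several readings did not fully reproduce it. Scenario D states 9.1 subjects and 2.0 cohorts; the re-runs gave 10 to 17 and 2.2 to 3.6. Table 13 therefore neither confirms nor excludes pooling.

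None of this makes the printed step consistent with section 4.2.1.3.

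**Conclusion.** The rule is wrong as written, in a bounded sense. On the natural reading of QS_d, the top level holds 48% of the prior against at most 5.6% elsewhere. It remains the maximum for 1/3, 2/4, 2/5 and 3/5 at 2.5, 4, 5.5 and 6.5 GBq. For 2/4 and 2/5 this holds under both one-record and two-record coding. The model step hardly discriminates, constraints (a) to (c) set the dose, and they say nothing about 2/4 and 2/5 although 3/6 is capped. The rule can return a level above the 33% limit, but does not always: about 26% or 41% in the worked 2/4 case.

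This rests on the stated priors and model, no DLTs at earlier planned levels, and pooling at 7.5 GBq. The documents do not support the stronger conclusions that overdosing will follow automatically, that pooling alone explains escalation, or that Table 13 was run with this defect.

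**What to change.** Reconcile 19.5.1 and 19.5.2 with section 4.2.1.3:

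1. State how QS_d is computed at 7.5 GBq and whether it uses the posterior distribution of the DLT rate or its mean. Do the same for QC_d at the top cumulative level, which feeds the Cycle 2 rule; Table 11 puts 27.2% of the prior MTCA above 15 GBq.
2. State how Cycle 1 and Cycle 2 records enter the likelihood.
3. Correct the model step so that it agrees with the stated 33% limit.
4. Complete the constraint list for every reachable count, including 2/4 and 2/5.
5. Rerun Table 13 under the corrected rule.

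The content of the dose rule is for the sponsor and the SRC; none is proposed here. The cost is text edits in Attachment 5 and a simulation rerun, with no added subjects.
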